10.1.4 FUTURE USE OF STORED SPECIMENS AND DATA

Data collected for this study will be analyzed and stored at the NASH CRN Data Coordinating Center. After the study is completed, the de-identified, archived data will be transmitted to and stored at the NIDDK Central Repository, for use by other researchers including those outside of the study. Permission to transmit data to the NIDDK Central Repository will be included in the informed consent.

With the participant's approval and as approved by the single Institutional Review Boards (sIRB), de-identified biological samples will be stored at the NIDDK Central Biorepository with the same goal as the sharing of data with the NIDDK Central Repository. These samples could be used to research the causes of NASH, its complications and other conditions for which individuals with NASH are at increased risk, and to improve treatment. The NIDDK Central Repository will also be provided with a code-link that will allow linking the biological specimens with the phenotypic data from each participant, maintaining the blinding of the identity of the participant.

During the conduct of the study, an individual participant can choose to withdraw consent to have biological specimens stored for future research. However, withdrawal of consent with regard to biosample storage may not be possible after the study is completed.

When the study is completed, the NIDDK Central Repository will provide oversight for the access to and use of study data and/or samples.

10.1.6 SAFETY OVERSIGHT

Safety oversight will be under the direction of a Data and Safety Monitoring Board (DSMB) composed of individuals with the appropriate expertise, including gastroenterology, hepatology, cardiology and statistics. Members of the DSMB are independent from the study conduct and free of conflict of interest, or measures should be in place to minimize perceived conflict of interest.

An Independent Medical Monitor and an independent Data and Safety Monitoring Board (DSMB), appointed by the NIDDK, will review the protocol for the VEDS trial and monitor the safety data as the trial progresses to ensure patient safety and to review efficacy. The DSMB is a multidisciplinary group with a written charge provided by the NIDDK. The DSMB reports to the NIDDK, which will communicate DSMB recommendations to the investigators, as appropriate. The DSMB will hold a meeting to approve the protocol. The DSMB will review performance and safety data. The DSMB may request more frequent meetings if necessary to fulfill its charge. It may also request additional safety reports on a more frequent basis. For example, all serious adverse events are reported to the DSMB for their consideration and recommendations as they occur.

Interim data on safety measures requested by the DSMB are reviewed at each of the scheduled semi-annual full meetings. Serious adverse events will be reviewed by the DSMB as they occur with the option of a teleconference discussion if any DSMB member so requests.

The DSMB will review quarterly reports by masked treatment groups of incident hepatotoxicities, as well as counts of patients who required more frequent liver function testing due to rises in ALT levels of more than 2 times baseline ALT or beyond 300 U/L. The DSMB will also examine the trends in ALT or AST levels for each patient who experiences a rise in ALT.

The DSMB also reviews the overall progress of the trial in terms of recruitment and data quality and makes a formal recommendation to the NIDDK at the end of each scheduled meeting as to whether the trial should continue unmodified, continue with protocol modifications, or be stopped.

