6.3 MEASURES TO MINIMIZE BIAS: RANDOMIZATION AND BLINDING

Randomization: The randomization scheme will assign patients into four groups to receive vitamin E at 133.4 mg (200 IU), 266.8 mg (400 IU), or 533.6 mg (800 IU) or placebo daily. The randomization design will be stratified by clinical center with assignments in permuted blocks of random length within each clinic. This scheme will ensure that the four groups will be balanced by calendar time of randomization (to minimize secular effects) and by clinic (to minimize clinic-specific effects of differences in patient populations and management).

The randomization plan will be prepared and administered centrally by the Data Coordinating Center (DCC) but will not require real time interaction with a DCC staff member. Requests for randomizations will be made by the clinics using a web-based application. An assignment will be issued only if the database shows that the patient is eligible, has signed the consent statement, and has had all required baseline data keyed into the database.

Treatment assignments are double masked throughout the study until all data collection for the VEDS trial has been completed (i.e., after completion of the post-trial follow-up for all participants). Every effort will be made to maintain the masking throughout the study except in emergencies. The code of specific pharmacological treatment will not be broken without the knowledge of the clinical center's principal investigator and the study leadership.

Unmasking of study medication may occur under the following conditions:

- **Severe allergic reaction (Stevens-Johnson Syndrome):** Study medication is stopped indefinitely. The patient, primary care provider (PCP), and the investigator may be unmasked.
- **Pregnancy during the study:** Study medication will be stopped indefinitely, and the coded medication may be unmasked. The patient, PCP, and investigator will be notified of the associated risks of teratogenicity.
- **Development of hepatotoxicity:** The drug induced liver injury (DILI) criteria described in section 7.1 will be used to define hepatotoxicity for this study. Study medication will be discontinued; however, there will be no unmasking until study conclusion.
- **Development of serious bleeding:** Serious bleeding will be defined as bleeding associated with a serious adverse event (SAE) (see section 8.3.2). The patient, primary care provider (PCP), and the investigator may be unmasked.

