The Data and Safety Monitoring Board will review all instances of unmasking that occur.

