8.3.5 ADVERSE EVENT REPORTING

Adverse events will be recorded on study data forms whether or not they are thought to be associated with the study or with the study drug. Adverse events may be discovered during regularly scheduled visits or through unscheduled patient contacts between visits.

Summary data on adverse events will be monitored by the DSMB quarterly and at its semiannual meetings or more frequently, as needed. These summaries will include analyses comparing rates of adverse events by treatment group, by clinic, or in other subgroups requested by the DSMB. Where applicable, signs and symptoms associated with the adverse event will be graded as to severity by the clinical site staff as mild, moderate, or severe using Version 5.0 of the National Cancer Institute's Common Terminology Criteria for Adverse Events (CTCAE).[82]

After each DSMB meeting, the NIDDK will issue a written summary of the review of the study data, including adverse events, for transmission to the sIRB. Analyses or listings of adverse events will not be provided to the sIRB; however, adverse events involving unanticipated problems involving risks to patients, or breaches of protocol which might entail risk to patients must be reported to the sIRB and, as required, to the local IRB as soon as possible after they are discovered. Each participating center is responsible for ensuring that all sIRB and local IRB requirements for reporting adverse events are met.

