9.4.4 SAFETY ANALYSES

Safety data will be presented by treatment group to the Data and Safety Monitoring Board during the course of the trial. Each adverse event will be displayed showing AE name per the CTCAE v5.0 when applicable, class, severity, patient ID, clinic, treatment group, time since randomization, resolution status and physician's assessment of relatedness to treatment. Patient-specific summary tables including any adverse event (yes vs no), frequency of multiple adverse events (i.e., 0, 1, 2, 3+) and highest severity of adverse event (none, mild, moderate, severe, life-threatening) will be displayed by treatment group along with p-values from Fisher's exact tests.

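### The safety comparisons planned for the DSMB ignore dose order, so a harm that rises with dose is harder to detect than it need be in this four-dose trial.

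*Combined protocol and SAP*

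**What the plan says.** Three sections of the combined protocol and SAP describe what the DSMB receives.

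- Section 10.1.6 (Safety Oversight): "The DSMB will review quarterly reports by masked treatment groups of incident hepatotoxicities". The coding scheme is not described. The same section adds "The DSMB will also examine the trends in ALT or AST levels for each patient who experiences a rise in ALT", and says of the board "It may also request additional safety reports on a more frequent basis".
- Section 9.4.4 (Safety Analyses): "Safety data will be presented by treatment group to the Data and Safety Monitoring Board during the course of the trial". Patient-level summary tables (any event, number of events, highest severity) "will be displayed by treatment group along with p-values from" Fisher's exact tests. The word masked does not appear.
- Section 8.3.5 (Adverse Event Reporting): "These summaries will include analyses comparing rates of adverse events by treatment group, by clinic, or in other subgroups requested by the DSMB". No test is named, and masking is again not mentioned.

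Section 6.3 keeps assignments masked until data collection ends and states no exception for the DSMB. In its list of conditions for unmasking an individual, it says of hepatotoxicity that "there will be no unmasking until study conclusion". It also says "The Data and Safety Monitoring Board will review all instances of unmasking that occur". No section gives the board a route to the treatment codes, and none plans a dose-ordered safety comparison.

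**The concern.** The four arms are ordered, and the efficacy analysis uses that order through Williams' test (sections 9.2 and 9.4.2). Safety does not, although section 2.3.3 justifies the trial partly by the hope that a lower effective dose would avoid long-term adverse effects. A rise in events from placebo through 200 and 400 to 800 IU is a pattern that helps to separate a drug effect from chance.

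Two features of the plan leave that pattern unused. Fisher's exact test treats the arms as unordered categories even when they are identified. The liver report is by masked group, so if the codes do not carry dose order, the board cannot run a valid trend test of its own from that report. At stake is the board's sensitivity to a dose-related liver or bleeding signal while participants are still on treatment.

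**Working it through.** **Inputs.** From the documents: four arms, 50 per arm (section 9.2) and doses 0/200/400/800 IU. The documents give no expected rate of hepatotoxicity or bleeding and no power figure for safety, so there is no plan figure to reproduce. All event rates below are assumptions, listed in the order placebo/200/400/800 IU. Tests are two-sided at 5%.

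**Formulas.** With counts x_i, n = 50 per arm, pooled rate p and scores s = 0, 1, 2, 4 (dose in units of 200 IU, mean 1.75):

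- ordered (Cochran-Armitage): z = Σ x_i(s_i − 1.75) / √[p(1−p)·n·Σ(s_i − 1.75)²]
- unordered (chi-square, 3 df, standing in for Fisher's test): Q = Σ(x_i − np)² / [np(1−p)]

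**One table by hand.** Counts 1/2/4/7 of 50 give p = 14/200 = 0.07 and p(1−p) = 0.0651.

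- Ordered: numerator −1.75 − 1.50 + 1.00 + 15.75 = 13.5. Variance 0.0651 × 50 × 8.75 = 28.48. z = 13.5/5.34 = 2.53. The exact one-sided trend p is 0.009.
- Unordered: np = 3.5, so Q = (6.25 + 2.25 + 0.25 + 12.25)/3.255 = 21/3.255 = 6.45, p about 0.09. Fisher's exact p is 0.12.

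The same data are suggestive when read in dose order and unremarkable when not.

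**Power by simulation, rates rising with dose.**

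| Assumed rates (%) | Ordered trend | Unordered | Gap (points) |
|---|---|---|---|
| 2/4/7/14 | 72% | 52% | 20 |
| 4/6/10/18 | 72% | 55% | 17 |
| 2/5/10/20 | 91% | 80% | 11 |
| 10/15/20/30 | 76% | 60% | 16 |

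An exact calculation with Fisher's test itself, against a one-sided 2.5% exact trend test, shows the same pattern: 67% against 51% at 2/4/8/14%, and 88% against 78% at 2/6/10/20%.

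**Other shapes.**

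| Assumed rates (%) | Ordered trend | Unordered |
|---|---|---|
| 2/12/12/12 | 27% | 38% |
| 2/2/15/15 | 81% | 85% |
| 2/2/2/15 | 86% | 79% |
| 1/2/3/5 | about 25% | 12% |

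The trend test loses when harm is already complete at the lowest dose. When events are rare, both tests are poor.

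**Earlier looks.** At 25 per arm, 2/4/7/14% gives 44% against 24%. The gap remains, but neither test is reliable.

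**False alarms.** With 5% in every arm, the trend test flags 4.8% and the chi-square 4.0%. Flagging when either is significant gives about 7% at a single look. Guessing the code order is no substitute: taking the best trend over all 24 orders flags about 24%.

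**The case against.** The strongest reply is that the board is far from blind. Coded arms are still separate arms, and an unordered test has 52% to 80% power in the rising scenarios above. Only the liver report is called masked. Sections 8.3.5 and 9.4.4 give adverse events by treatment group without that word, so the dose order of bleeding and other events may already be known to the board. The board may ask for further reports, and it works under a written charge from the NIDDK that is not part of these documents and may deal with access to the codes. Nor is the board the only protection: there is an Independent Medical Monitor (10.1.6), a Safety Officer review of SAEs (8.3.6), and site rules for stopping study drug (7.1). All of this stands.

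It is also fair to say that masking the liver report has a purpose. ALT is both the liver-injury marker and the primary endpoint, section 10.1.6 has the board review efficacy, and section 9.4.2 lets it judge which confounders enter sensitivity analyses. Dose-labelled liver columns would give arm-level ALT information to a body with some say in the efficacy analysis. That is a reason not to make labels compulsory.

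Finally, removing the mask would not by itself gain power, because Fisher's test ignores order with or without labels. This is correct, and it is why the remedy is the added test. None of these points supplies a dose-ordered safety comparison.

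**Conclusion.** The point holds as a cheap improvement. Under assumed rates that rise with dose, leaving out an ordered test costs about 11 to 20 points of power at 50 per arm. That size depends on the assumed rates and shapes, on full enrolment and on a single look. Under a plateau the trend test is the weaker of the two (27% against 38% at 2/12/12/12%), so it belongs beside Fisher's test.

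A reader might infer more, and the documents do not support it:

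- That a dose-related harm cannot be seen by the DSMB. Arm-level excesses remain visible and testable, with less power.
- That all the board's safety data are masked. The word is attached only to the quarterly liver report. The status of the other reports, bleeding included, is unstated.
- That the codes are known to hide dose order, or that the board is refused them. The documents are silent on both.
- That one serious bleed would reveal an arm to the board. Section 6.3 only permits unmasking of the patient, primary care provider and investigator in that case, and says the board reviews such instances.

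**What to change.** 1. In sections 9.4.4 and 10.1.6, add a dose-ordered p-value (Cochran-Armitage or an exact trend test, scores proportional to 0/200/400/800 IU) beside Fisher's exact test for hepatotoxicity and bleeding counts in the closed DSMB reports. The Data Coordinating Center prepares and administers the randomization (section 6.3), so its statistician can compute this even if the report columns stay coded.
2. State in sections 8.3.5, 9.4.4 and 10.1.6, in the same terms, whether the DSMB sees coded or identified arms, and how it can obtain the codes. Whether columns carry dose labels is for the sponsor and the DSMB to settle.

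The cost is a few lines of text and one extra column in a closed report. Sample size, visits and masking at the sites do not change. There are two downsides. The board sees one more unadjusted p-value at each look (about 7% flagged by either test under no effect at a single look, and more over repeated looks), so the text should call these p-values descriptive. A small trend p-value shown with coded columns may also hint at which arm is which.

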10.1.7 CLINICAL MONITORING

Clinical site monitoring is conducted to ensure that the rights and well-being of trial participants are protected, that the reported trial data are accurate, complete, and verifiable, and that the conduct of the trial is in compliance with the currently approved protocol/amendment(s), with International Conference on Harmonisation Good Clinical Practice (ICH GCP), and with applicable regulatory requirement(s).

- Monitoring for this study will be performed by the NASH CRN DCC.
- To ensure data quality, the DCC will incorporate into the data entry programs a series of edit checks, including range checks, logic checks (e.g., skip patterns), and consistency checks, both within a data form and across forms. These integral checks are designed to detect deficiencies in the data before they are saved into the study database, so that the deficiencies may be easily and accurately corrected as they are being entered. In addition, the DCC will perform frequent computerized edit checks on entered data. The DCC will also perform ongoing comparisons of copies of source documents with the databases to ensure that data entered into the data system reflect those recorded on the source documents. Such database validations will help to pinpoint problems that cannot be detected by computer editing and may be used to guide increased scrutiny when needed. Any data queries identified will be flagged for action by the clinical site until resolved.
- The data system will maintain a clear and complete audit trail of all changes to the study databases. All changes to data forms will be documented appropriately on the source document and entered into NASH CRN data system. All forms entered and/or edited in the data system will be identified by the PIN of the operator, the network address (the "IP" address) of the computer being used, and the date and time of the operation. Records will not be deleted but rather marked as having been superseded.
- Performance monitoring: The web-based data system will allow for real-time reporting of most recruitment and data management activities. However, additional performance reports will be generated and circulated monthly and typically reviewed at each Steering Committee (SC) meeting. These reports include several key indicators of study performance, including counts of patients screened and randomized, of completed visits and of missing key data, of missed visits, and statistics summarizing performance with respect to timeliness of data entry and response to data queries.
- The SC and the DSMB will conduct a formal review of the study by webinar twice a year and will address quality assurance as part of their agenda. These committees will have responsibility for recommending corrective actions based on the performance data. It is anticipated that the primary responsibility for formulating and implementing these actions will reside in the SC. Potential actions might include specific recommendations for training, redistribution of study resources, or possibly termination of support for a center.
- Independent audits outside the DCC will not be conducted.

10.1.8 QUALITY ASSURANCE AND QUALITY CONTROL

Each clinical site will perform internal quality management of study conduct, data and biological specimen collection, documentation and completion.

Quality control (QC) procedures will be implemented beginning with the data entry system and data QC checks that will be run on the database will be generated. Any missing data or data anomalies will be communicated to the site(s) for clarification/resolution.

Following written Standard Operating Procedures (SOPs), the NASH CRN monitors will verify that the clinical trial is conducted and data are generated and biological specimens are collected, documented (recorded), and reported in compliance with the protocol, International Conference on Harmonisation Good Clinical Practice (ICH GCP), and applicable regulatory requirements (e.g., Good Laboratory Practices (GLP), Good Manufacturing Practices (GMP)).

The investigational site will provide direct access to all trial related sites, source data/documents, and reports for the purpose of monitoring and auditing by the NASH CRN, and inspection by local and regulatory authorities.

10.1.9 DATA HANDLING AND RECORD KEEPING

10.1.9.1 DATA COLLECTION AND MANAGEMENT RESPONSIBILITIES

Data collection is the responsibility of the clinical trial staff at the site under the supervision of the site investigator. The investigator is responsible for ensuring the accuracy, completeness, legibility, and timeliness of the data reported.

All source documents should be completed in a neat, legible manner to ensure accurate interpretation of data.

Hard copies of the study visit worksheets will be printed by clinics for use as source document worksheets for recording data for each participant enrolled in the study. Data recorded in the electronic case report form (eCRF) derived from source documents should be consistent with the data recorded on the source documents.

Clinical data (including adverse events (AEs), concomitant medications, and expected adverse reactions data) and clinical laboratory data will be entered into the 21 CFR Part 11-compliant electronic data capture system. The data system includes password protection and internal quality checks, such as automatic range checks, to identify data that appear inconsistent, incomplete, or inaccurate. Clinical data will be entered directly from the source documents.

10.1.9.2 STUDY RECORDS RETENTION

Under the HIPAA Privacy rule, investigators must maintain study records for 7 years after the study ends or 7 years after the last disclosure of identifiable health information from study records, whichever is later.

10.1.10 PROTOCOL DEVIATIONS

A protocol deviation is any noncompliance with the clinical trial protocol, International Conference on Harmonisation Good Clinical Practice (ICH GCP), or Standard Operating Procedures (SOP) requirements. The noncompliance may be either on the part of the participant, the investigator, or the study site staff. As a result of deviations, corrective actions are to be developed by the site and implemented promptly.

These practices are consistent with ICH GCP:

- 4.5 Compliance with Protocol, sections 4.5.1, 4.5.2, and 4.5.3
- 5.1 Quality Assurance and Quality Control, section 5.1.1
- 5.20 Noncompliance, sections 5.20.1, and 5.20.2.

It is the responsibility of the site investigator to use continuous vigilance to identify and report deviations within 5 working days of identification of the protocol deviation, or within 10 working days of the scheduled protocol-required activity. All deviations must be addressed in study source documents and reported to NIDDK Program Official and the Data Coordinating Center. Protocol deviations must be sent to the reviewing single Institutional Review Board (sIRB) and the local Institutional Review Board (IRB) per their policies. The site investigator is responsible for knowing and adhering to the reviewing sIRB and local IRB requirements. Further details about the handling of protocol deviations will be included in the SOP.

